9. STUDY SIZE

Phase I of the study (descriptive)

Not applicable as there are no specified *a priori* hypotheses

Phase II of the study (comparative)

- The estimated number of incident patients with VTE and no history of active cancer from the 2018 HIRA-National Patient Sample (HIRA-NPS) database is 1,465, where the HIRA-NPS database is a 3% random sample of the entire Korean population of 50 million. Based on this estimation, the projected number of patients with VTE from the entire Korean population (HIRA database) of 2018 is 48,828 (1,465 * 33.33).
 - Excluding period for patients with previous OAC treatment, VTE history or a history of active cancer was set to prior 3 months because HIRA NPS database used in sample size estimation was constituted of one-year data only.

1) Apixaban vs. warfarin

- Among the above-mentioned number of incident patients with VTE and no history of active cancer, those who newly initiated apixaban or warfarin was estimated to be 211 patients (14.4%; 211/1,465), where patients had no prescription for OACs and no history of VTE within the 3-month period prior to VTE diagnosis. From these 211 patients, there were 83 (39.3%) apixaban users and 128 (60.7%) warfarin users (based on 2018 HIRA-NPS data). Hence, the projected number of patients with VTE who newly initiated OACs to be present in the HIRA database in a single year is 7,032 patients (apixaban 2,766; warfarin 4,266). As this study aims to utilize data from 2013 to 2019 (7 years), the final projected number of patients with VTE who newly initiated apixaban or warfarin from the HIRA database is 49,224 patients (apixaban 19,362; warfarin 29,862).
- Considering a 95% for a two-sided CI level (α -error=0.05) and 80% power, the sample size for the comparative safety study for major bleeding events was calculated based on the following components:
 - HR for major bleeding events from previous literature: 0.31-0.75
 - Overall probability of major bleeding events from previous literature: 1.19%
 - Proportion of apixaban users among patients with VTE from the 2018 HIRA-NPS database: 39.3% (83 apixaban users; 128 warfarin users).
 - 2,013 patients with VTE treated with apixaban or warfarin are required to detect at 5% α -error, and 80% statistical power, and HR of 0.31 by sample size calculations for survival analysis; alternatively (more conservative estimate), 33,340 patients with VTE treated with apixaban or warfarin are required to detect at 5% α -error, and 80% statistical power, and HR of 0.75 by sample size calculations for survival analysis.
 - As this study is expected to include 49,224 patients with VTE, with 19,362 patients treated with apixaban from the nationwide HIRA database, this study will have enough statistical power to test the hypothesis of the association between apixaban use and risk of bleeding events among patients with VTE.

2) Rivaroxaban vs. warfarin

- Among the above-mentioned number of incident patients with VTE and no history of active cancer, those who newly initiated rivaroxaban or warfarin was estimated to be 382 patients (26.1%; 382/1,465), where patients had no prescription for OACs and no history of VTE within the 3-month period prior to VTE diagnosis. From these 382 patients, there were 264 (69.1%) rivaroxaban users and 118 (30.9%) warfarin users (based on 2018 HIRA-NPS data). Hence, the projected number of patients with VTE who newly initiated OACs to be present in the HIRA database in a single year is 12,732 patients (rivaroxaban 8,799; warfarin 3,933). As this study aims to utilize data from 2013 to 2019 (7 years), the final projected number of patients with VTE who newly initiated rivaroxaban or

warfarin from the HIRA database is 89,124 patients (rivaroxaban 61,593; warfarin 27,531).

- Considering a 95% for a two-sided CI level (α -error=0.05) and 80% power, the sample size for the comparative safety study for major bleeding events was calculated based on the following components:
 - HR for major bleeding events from previous literature: 0.77-1.19
 - Overall probability of major bleeding events from previous literature: 8.1%
 - Proportion of rivaroxaban users among patients with VTE from the 2018 HIRA-NPS database: 69.1% (264 rivaroxaban users; 118 warfarin users).
 - 6,630 patients with VTE treated with rivaroxaban or warfarin are required to detect at 5% α -error, and 80% statistical power, and HR of 0.77 by sample size calculations for survival analysis; alternatively (more conservative estimate), 14,967 patients with VTE treated with rivaroxaban or warfarin are required to detect at 5% α -error, and 80% statistical power, and HR of 1.19 by sample size calculations for survival analysis.
 - As this study is expected to include 89,124 patients with VTE, with 61,593 patients treated with rivaroxaban from the nationwide HIRA database, this study will have enough statistical power to test the hypothesis of the association between rivaroxaban use and risk of bleeding events among patients with VTE.

3) Edoxaban vs. warfarin

- Among the above-mentioned number of incident patients with VTE and no history of active cancer, those who newly initiated edoxaban or warfarin was estimated to be 184 patients (12.6%; 184/1,465), where patients had no prescription for OACs and no history of VTE within the 3-month period prior to VTE diagnosis. From these 184 patients, there were 57 (31.0%) edoxaban users and 127 (69.0%) warfarin users (based on 2018 HIRA-NPS data). Hence, the projected number of patients with VTE who newly initiated OACs to be present in the HIRA database in a single year is 6,132 patients (edoxaban 1,900; warfarin 4,232). As this study aims to utilize data from 2013 to 2019 (7 years), the final projected number of patients with VTE who newly initiated edoxaban or warfarin from the HIRA database is 42,924 patients (edoxaban 13,300; warfarin 29,624).
- Considering a 95% for a two-sided CI level (α -error=0.05) and 80% power, the sample size for the comparative safety study for major bleeding events was calculated based on the following components:
 - HR for major bleeding events from previous literature: 0.56-0.81
 - Overall probability of major bleeding events from previous literature: 8.5%

- Proportion of edoxaban users among patients with VTE from the 2018 HIRA-NPS database: 31.0% (57 edoxaban users; 127 warfarin users).
- 1,282 patients with VTE treated with edoxaban or warfarin are required to detect at 5% α -error, and 80% statistical power, and HR of 0.56 by sample size calculations for survival analysis; alternatively (more conservative estimate), 9,703 patients with VTE treated with edoxaban or warfarin are required to detect at 5% α -error, and 80% statistical power, and HR of 0.81 by sample size calculations for survival analysis.
- As this study is expected to include 42,924 patients with VTE, with 13,300 patients treated with edoxaban from the nationwide HIRA database, this study will have enough statistical power to test the hypothesis of the association between edoxaban use and risk of bleeding events among patients with VTE.

4) Dabigatran vs. warfarin

- Among the above-mentioned number of incident patients with VTE and no history of active cancer, those who newly initiated dabigatran or warfarin was estimated to be 155 patients (10.6%; 155/1,465), where patients had no prescription for OACs and no history of VTE within the 3-month period prior to VTE diagnosis. From these 155 patients, there were 26 (16.8%) dabigatran users and 129 (83.2%) warfarin users (based on 2018 HIRA-NPS data). Hence, the projected number of patients with VTE who newly initiated OACs to be present in the HIRA database in a single year is 5,166 patients (dabigatran 866; warfarin 4,299). As this study aims to utilize data from 2013 to 2019 (7 years), the final projected number of patients with VTE who newly initiated dabigatran or warfarin from the HIRA database is 36,162 patients (dabigatran 6,062; warfarin 30,093).
- Considering a 95% for a two-sided CI level (α -error=0.05) and 80% power, the sample size for the comparative safety study for major bleeding events was calculated based on the following components:
 - HR for major bleeding events from previous literature: 0.52-0.69
 - Overall probability of major bleeding events from previous literature: 1.4%
 - Proportion of dabigatran users among patients with VTE from the 2018 HIRA-NPS database: 16.8% (26 dabigatran users; 129 warfarin users).
 - 9,361 patients with VTE treated with dabigatran or warfarin are required to detect at 5% α -error, and 80% statistical power, and HR of 0.52 by sample size calculations for survival analysis; alternatively (more conservative estimate), 29,071 patients with VTE treated with edoxaban or warfarin are required to detect at 5% α -error, and 80% statistical power, and HR of 0.69 by sample size calculations for survival analysis.
 - As this study is expected to include 36,162 patients with VTE, with 6,062 patients treated with dabigatran from the nationwide HIRA database, this

study will have enough statistical power to test the hypothesis of the association between dabigatran use and risk of bleeding events among patients with VTE.

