5. INTRODUCTION

Venous Thromboembolism (VTE), which includes deep vein thrombosis (DVT) and pulmonary embolism (PE), is a major cause of morbidity, mortality and healthcare expenditure. Although the occurrence of VTE in the Asian population has been lower than in Western populations, Its incidence has been reported to have increased rapidly in recent years.

For pharmacologic treatment of patients with VTE without cancer, the American College of Chest Physicians (CHEST) guidelines recommend the use of Non-Vitamin K antagonist oral anticoagulants (NOACs) over Vitamin K Antagonists (VKAs), with supporting evidences suggesting that each NOAC (e.g., apixaban) is effective at preventing recurrent VTE. In more recent treatment guidelines for the management of VTE released by the American Society of Hematology (ASH), NOACs are still recommended over VKAs for the initial management of VTE. NOACs are classified as new generation of anticoagulants with approved indications of the risk reduction of stroke and embolism in nonvalvular atrial fibrillation (NVAF) as well as prophylaxis and treatment of DVT and PE.

All NOACs became available as the first-line treatment of acute VTE in Korea after reimbursement expansion in May 2015. However, despite the increasing use of NOACs among VTE patients, there are still limited real-world evidence that assess treatment patterns as well as effectiveness and safety of the different anticoagulants especially among Asian population.

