6. RESEARCH QUESTION AND OBJECTIVES

Research Question

What is the real-world evidence of anticoagulant treatment for patients with VTE that can be found in the nationwide claims database in Korea? The current study will take place in two phases:

Phase I involves a descriptive assessment of patient characteristics and treatment patterns in Korea as well as detailed power calculations for comparative study.

Phase II involves analyses of comparative safety between each NOAC and warfarin. These analyses will be implemented if there is sufficient power to enable scientifically valid inferences.

Primary Objectives of Phase I of the study

- To describe the sociodemographic and clinical characteristics of patients with VTE, overall and according to their index VTE treatment (parenteral anticoagulants [PAC] only, warfarin-based, NOAC-based)To describe index anticoagulant treatment patterns by investigating the utilization of different

anticoagulants, treatment interruption, switches, discontinuations, and overall treatment duration

Primary Objective of Phase II of the study

- To describe and compare the risk of clinical outcome (major bleeding) according to the specific type of OAC

[NOTE] Comparative analyses, especially NOAC vs NOAC direct comparisons, will be performed contingent on a feasibility assessment based on the descriptive analyses and the agreed opinion on scope after discussion with Eliquis Alliance Real World Data Review Committee.

Secondary objective of Phase I of the study

- To explore the relevant clinical events preceding treatment change from index anticoagulant

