8.2. Study population

The study cohort will be defined as patients diagnosed with VTE between 1 Mar 2013 and 30 Jun 2019. The cohort entry will be defined as the date of incident VTE diagnosis. The index date will be defined as the date of first prescription for anticoagulants within 30 days after the index VTE event. The length of the exclusion assessment window will vary depending on the condition, from 12-months at minimum to anytime prior to index date. The following patients will be excluded: A record of VTE diagnosis within the 12-month period prior to the index VTE encounter, diagnosed with atrial fibrillation, atrial flutter, mechanical heart valve replacement or mitral stenosis anytime prior to index date, had a record of Inferior Vena Cava filter anytime prior to index date, received anticoagulatory therapy within the 12-month period prior to index VTE encounter to restrict to new users of anticoagulatory therapy, prescribed two different anticoagulants on the same index date to prevent exposure misclassification, had a record of pregnancy within the 9-month period prior to index date, and for the Phase II of the study only, had a record of active cancer within six months period prior to index date.

Baseline sociodemographic characteristics (e.g., age, sex) will be assessed on the index date, whereas clinical characteristics (comorbidities, previous use of medications, Charlson comorbidity index [CCI], HAS-BLED scores, initial presentation of VTE, number of outpatient visits) will be assessed in the 6-month period prior to the index date except when otherwise specified in section 8.4 *Variables* (Figure 2).

Within this study cohort, we will describe the treatment patterns of anticoagulants prescribed for VTE treatment throughout the period of follow-up, defined as the period from the index date to the end of the study period. Moreover, if feasible, we will also examine the risk of major bleeding overall and by site, associated with each NOAC use, as compared with warfarin.

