8.3. Setting

8.3.1. Inclusion criteria

Patients must meet all of the following inclusion criteria to be eligible for inclusion in the study:

1. Incident VTE diagnosis in an inpatient or outpatient setting (International Classification of Diseases 10th Revision [ICD-10]: I26.0, I26.9, I80.2, I80.3) between 1 Mar 2013 and 30 Jun 2019
2. Received anticoagulation therapy (all medication codes for anticoagulants approved for VTE in Korea; unfractionated heparin [UFH], low molecular weight heparin [LMWH], warfarin, and NOACs) within 30 days of their VTE diagnosis (the index date will be defined as the date of treatment initiation with anticoagulants)
3. Aged ≥ 18 years at index date

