13. LIST OF FIGURES

Figure 1. Kaplan-Meier plot showing time to anticoagulant therapy interruption in patients with venous thromboembolism according to presence of active cancer.	65
Figure 2. Kaplan-Meier plot showing time to anticoagulant therapy switching in patients with venous thromboembolism according to presence of active cancer.	66
Figure 3. Kaplan-Meier plot showing time to anticoagulant therapy discontinuation in patients with venous thromboembolism according to presence of active cancer.	67
Figure 4. Trends in newly prescribed anticoagulants in patients with venous thromboembolism between Mar 2013 and Jun 2019.....	68
Figure 5. Cumulative incidence curves for the risk of major bleeding events associated with NOAC use versus warfarin	69
Figure 6. Number of weighted events, incidence rate, and hazard ratio of major bleeding events associated with NOAC use versus warfarin.	70

[figure not shown]

Figure 1. Kaplan-Meier plot showing time to anticoagulant therapy interruption in patients with venous thromboembolism according to presence of active cancer.

[figure not shown]

Figure 2. Kaplan-Meier plot showing time to anticoagulant therapy switching in patients with venous thromboembolism according to presence of active cancer.

[figure not shown]

Figure 3. Kaplan-Meier plot showing time to anticoagulant therapy discontinuation in patients with venous thromboembolism according to presence of active cancer.

[figure not shown]

Figure 4. Trends in newly prescribed anticoagulants in patients with venous thromboembolism between Mar 2013 and Jun 2019.

[figure not shown]

Figure 5. Cumulative incidence curves for the risk of major bleeding events associated with NOAC use versus warfarin

PFIZER CONFIDENTIAL

[figure not shown]

Figure 6. Number of weighted events, incidence rate, and hazard ratio of major bleeding events associated with NOAC use versus warfarin.

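### The Phase II cohort projections use seven years of accrual, but the entry window is 6.33 years, so all four totals and all eight arm sizes are 10.5% too high (minor; no power statement is overturned)

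*SAP*

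**What the plan says.** SAP section 9 takes the 2018 count of new users in the 3% patient sample, multiplies it by 33.33 to get an annual national count, and then extends it to the study: "As this study aims to utilize data from 2013 to 2019 (7 years), the final projected number of patients with VTE". This is done for each of the four NOAC-versus-warfarin comparisons. Protocol section 4 (Abstract, Study size) and Protocol section 9.5 carry the same text and figures.

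Cohort entry is defined differently. SAP section 8.2 states: "The study cohort will be defined as patients diagnosed with VTE between 1 Mar 2013 and 30 Jun 2019". The first inclusion criterion (SAP section 8.3.1) gives the same dates, "between 1 Mar 2013 and 30 Jun 2019", as do Protocol sections 9.1 and 9.2.1. The planned trend figure in SAP section 13 covers the same span: "Trends in newly prescribed anticoagulants in patients with venous thromboembolism between Mar 2013 and Jun 2019". The index date is the first anticoagulant prescription within 30 days after the VTE event (SAP section 8.2).

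Each projected total is then compared with a required sample size, for example "33,340 patients with VTE treated with apixaban or warfarin are required to detect" a hazard ratio of 0.75. Each comparison closes with a statement that power will be sufficient.

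**The concern.** The multiplier counts seven full calendar years of new patients. The entry criteria open two months into 2013 and close halfway through 2019. The data extend beyond that window at both ends, but only for look-back and follow-up, so they add no patients. The projected totals and arm sizes are therefore too high wherever they appear.

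The four statements of adequate power cite these totals. If the surplus over the required size were thin, a 10.5% overstatement could hide a shortfall. Dabigatran has the smallest stated surplus, so it is the comparison to check first.

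**Working it through.** **Inputs (SAP section 9 unless noted)**
- Entry window: 1 Mar 2013 to 30 Jun 2019 (SAP sections 8.2 and 8.3.1).
- Annual counts, NOAC / warfarin: apixaban 2,766 / 4,266; rivaroxaban 8,799 / 3,933; edoxaban 1,900 / 4,232; dabigatran 866 / 4,299.
- Overall probability of major bleeding: 1.19%, 8.1%, 8.5% and 1.4%, in the same order.
- Conservative hazard ratio and required size: apixaban 0.75, 33,340; rivaroxaban 1.19, 14,967; edoxaban 0.81, 9,703; dabigatran 0.69, 29,071.
- Two-sided alpha 0.05, power 80%.

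**Step 1. Reproduce the stated totals.** Annual total × 7: 7,032 × 7 = 49,224; 12,732 × 7 = 89,124; 6,132 × 7 = 42,924; 5,166 × 7 = 36,162. All four match, and so do all eight arm sizes.

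**Step 2. Length of the entry window.** 10 months in 2013 + 60 months in 2014 to 2018 + 6 months in 2019 = 76 months; 76/12 = 6.333 years. Overstatement: 7/6.333 = 1.105, or 10.5% of the corrected figure. Cut from the stated figure: 1 − 6.333/7 = 9.5%.

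**Step 3. Rescale the arms** (annual count × 6.333) and compare with the required size.

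| Comparison | Stated total | Corrected total (NOAC + warfarin) | Required | Margin, stated → corrected |
|---|---|---|---|---|
| Apixaban | 49,224 | 44,536 (17,518 + 27,018) | 33,340 | 48% → 34% |
| Rivaroxaban | 89,124 | 80,636 (55,727 + 24,909) | 14,967 | 495% → 439% |
| Edoxaban | 42,924 | 38,836 (12,033 + 26,803) | 9,703 | 342% → 300% |
| Dabigatran | 36,162 | 32,712 (5,485 + 27,227) | 29,071 | 24% → 13% |

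Margin = total / required − 1. For dabigatran, 36,162/29,071 = 1.244 and 32,712/29,071 = 1.125. The stated dabigatran annual total of 5,166 is one more than its arms, so scaling that total gives 32,718 instead of 32,712. That is rounding already in the plan.

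**Step 4. Power on the plan's own inputs.** Power = Φ(√(N·p·a·(1 − a))·|ln HR| − 1.96), with N the total, p the event probability and a the NOAC share. The same formula solved for N at 80% power gives 33,398, 15,000, 9,725 and 29,177. These are within 0.4% of the plan's four conservative required sizes, so the formula matches the plan's method closely.
- Apixaban, HR 0.75, a = 2,766/7,032 = 0.393: at 49,224, Φ(3.401 − 1.960) = 92.5%; at 44,536, Φ(3.235 − 1.960) = 89.9%.
- Dabigatran, HR 0.69, a = 866/5,165 = 0.168: at seven years, Φ(3.119 − 1.960) = 87.7%; at 32,712, Φ(2.966 − 1.960) = 84.3%.
- Rivaroxaban (HR 1.19) and edoxaban (HR 0.81): above 99.9% before and after.

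**The case against.** **The seven years may describe the data and not the accrual.** This does not work. The data period is 1 Mar 2012 to 31 Dec 2019, which is 94 months or 7.83 years. The months before March 2013 and after June 2019 cannot supply a diagnosis inside the entry window. Nothing in either document supports seven years of accrual.

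**No conclusion changes.** This stands. Every comparison keeps at least 84% power at its conservative hazard ratio, and no endpoint, population or analysis uses the multiplier. Sampling error matters more: the dabigatran rate rests on 26 sampled users. An exact Poisson 95% interval of about 17 to 38 on that count, with warfarin held at 27,227, moves power from about 70% to 93%, against 3.4 points for the window.

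**The plan already guards against a shortfall.** This also stands. Phase I includes detailed power calculations, and SAP section 6 says of the comparative analyses: "These analyses will be implemented if there is sufficient power to enable scientifically valid inferences". The projections do not decide whether Phase II runs.

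**The rescaled totals are still rough.** True. SAP section 9 discloses a 3-month look-back in the sample, whereas the study applies 12 months for prior VTE and anticoagulation. Restated figures should be rounded.

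**A stronger reading.** A reader might infer that the comparisons are underpowered because 2018 uptake is applied to years before NOACs were widely used. SAP section 5 says "All NOACs became available as the first-line treatment of acute VTE in Korea after reimbursement expansion in May 2015" and refers to limited evidence "despite the increasing use of NOACs among VTE patients". This shows that a constant 2018 rate is an unstated assumption. It does not show a shortfall. The documents give no counts for other years and do not say that no NOAC was started before May 2015. Patients who did not start a NOAC in the early years may have started warfarin, which would offset part of the loss. The size of the effect cannot be derived from the plan.

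**Conclusion.** The error is certain and small. All four totals and all eight arm sizes, in three places across the two documents, are 10.5% higher than the plan's own entry window supports. Power at the conservative hazard ratio drops by 2.6 points for apixaban and 3.4 points for dabigatran, and stays above 80% in all four comparisons. The correction alone overturns none of the adequacy statements; its main effect is to roughly halve the dabigatran margin.

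The power figures rest on the plan's event probabilities, hazard ratios and NOAC shares, and on the 2018 annual count holding in every entry year. They isolate the window error and are not a full re-projection. Severity: minor.

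**What to change.** In Protocol sections 4 and 9.5 and SAP section 9:

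1. Replace the seven-year multiplier with the 6.33-year entry window (1 Mar 2013 to 30 Jun 2019).
2. Restate the projections, rounded: apixaban comparison about 44,500 (17,500 + 27,000); rivaroxaban about 80,600 (55,700 + 24,900); edoxaban about 38,800 (12,000 + 26,800); dabigatran about 32,700 (5,500 + 27,200).
3. Add one sentence saying that these totals assume the 2018 HIRA-NPS rate in every entry year.
4. Refer the four adequacy statements to the Phase I power calculation already required by SAP section 6, using actual counts by index year. Both SAP Table 1 (warfarin-based) and SAP Table 3 (each NOAC) are needed, because Table 3 has no warfarin column.

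Do not write in uptake-based power ranges or fixed minimum numbers of starters; neither can be supported from the documents. The cost is arithmetic and wording only, with no change to design, data or analysis.

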- Among the above-mentioned number of incident patients with VTE and no history of active cancer, those who newly initiated dabigatran or warfarin was estimated to be 155 patients (10.6%; 155/1,465), where patients had no prescription for OACs and no history of VTE within the 3-month period prior to VTE diagnosis. From these 155 patients, there were 26 (16.8%) dabigatran users and 129 (83.2%) warfarin users (based on 2018 HIRA-NPS data). Hence, the projected number of patients with VTE

who newly initiated OACs to be present in the HIRA database in a single year is 5,166 patients (dabigatran 866; warfarin 4,299). As this study aims to utilize data from 2013 to 2019 (7 years), the final projected number of patients with VTE who newly initiated dabigatran or warfarin from the HIRA database is 36,162 patients (dabigatran 6,062; warfarin 30,093).

- Considering a 95% for a two-sided CI level (α -error=0.05) and 80% power, the sample size for the comparative safety study for major bleeding events was calculated based on the following components:
 - HR for major bleeding events from previous literature: 0.52-0.69
 - Overall probability of major bleeding events from previous literature: 1.4%
 - Proportion of dabigatran users among patients with VTE from the 2018 HIRA-NPS database: 16.8% (26 dabigatran users; 129 warfarin users).
 - 9,361 patients with VTE treated with dabigatran or warfarin are required to detect at 5% α -error, and 80% statistical power, and HR of 0.52 by sample size calculations for survival analysis; alternatively (more conservative estimate), 29,071 patients with VTE treated with edoxaban or warfarin are required to detect at 5% α -error, and 80% statistical power, and HR of 0.69 by sample size calculations for survival analysis.
 - As this study is expected to include 36,162 patients with VTE, with 6,062 patients treated with dabigatran from the nationwide HIRA database, this study will have enough statistical power to test the hypothesis of the association between dabigatran use and risk of bleeding events among patients with VTE.

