- In the NOAC-based group, all analyses will be repeated stratified by each individual NOAC class (e.g, apixaban, dabigatran, rivaroxaban, edoxaban) to

PFIZER CONFIDENTIAL

identify the difference in baseline characteristics and treatment patterns between each NOAC class.

- To identify potential reasons for treatment change, clinical events preceding the first treatment change (major bleeding, thromboembolism diagnosis, complications of VTE, major surgery, active cancer, a new diagnosis of CKD or AKI, a new diagnosis of liver disease or abnormal liver function) will be measured within 30 days prior to the first date of treatment change. Patients can contribute with multiple events.
- All analyses of treatment patterns will be presented stratified according to the index anticoagulant treatment, and not overall or per drug class.

Phase II of the study (comparative)

Propensity score analysis

- To balance and adjust for any potential differences in baseline sociodemographic and clinical characteristics between treatment groups, propensity score (PS) methods will be implemented.
 - A logistic regression model will be used to estimate the predicted probability (propensity) of initiating each NOAC compared with warfarin given baseline covariates mentioned above. By using the estimated PS, we will apply the PS based on the inverse probability of treatment weights (IPTW), where the treatment group of interest will be given a weight of 1/PS, and the comparator group will be given a weight of 1/(1-PS) [4, 5]. The most extreme 1% of PS values (IPTW with trimming) will be excluded to improve comparability between exposure groups.

Main Analysis

- Sociodemographic and clinical characteristics will be summarized with means (STD) or median (IQR) for continuous variables and with count (proportions) for categorical variables for the two treatment comparisons of: apixaban vs warfarin, rivaroxaban vs warfarin, edoxaban vs warfarin and dabigatran vs warfarin (and NOAC vs NOAC, if scientifically feasible).
 - Differences in baseline covariates between users of different OACs will be assessed using the SD where the absolute SD <0.1 will be considered as well balanced.
- The incidence rate of major bleeding overall and by site will be presented as the total number of events per 1,000 person-years, with its 95% CIs estimated using the Poisson distribution.

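### At its conservative HR of 0.69 the dabigatran–warfarin power claim has only a 24% margin, and it rests on an unweighted formula and on 2018 counts multiplied by seven

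*SAP*

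**What the plan says.** SAP section 9, part 4 (repeated in Protocol sections 4 and 9.5) sizes dabigatran against warfarin from an HR range of 0.52 to 0.69, a 1.4% overall probability of major bleeding and a 16.8% dabigatran share (26 of 155 patients in the 2018 sample). Its framing is "Considering a 95% for a two-sided CI level (α -error=0.05) and 80% power". For the conservative HR it states "29,071 patients with VTE treated with edoxaban or warfarin are required to detect at 5% α -error, and 80% statistical power, and HR of 0.69"; the drug named there is a slip, since the sentence sits in the dabigatran part and uses its inputs. One projected 2018 year (866 dabigatran, 4,299 warfarin) times seven gives "dabigatran 6,062; warfarin 30,093", in all 36,162 patients, and the section concludes that the "study will have enough statistical power to test the hypothesis of the association between dabigatran use and risk of bleeding events".

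Three other places bear on this:

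- SAP section 10 makes the main comparison a weighted Cox model in which "the treatment group of interest will be given a weight of 1/PS, and the comparator group will be given a weight of 1/(1-PS"), after the most extreme 1% of propensity scores (PS) are excluded.
- SAP section 8.2 enrols diagnoses from 1 Mar 2013 to 30 Jun 2019, while SAP section 5 says "All NOACs became available as the first-line treatment of acute VTE in Korea after reimbursement expansion in May 2015".
- SAP section 6 assigns to Phase I a descriptive assessment "as well as detailed power calculations for comparative study", and runs Phase II only if power is sufficient.

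**The concern.** The calculation describes a different study from the one planned, in two respects. It sizes an unweighted comparison, whereas the analysis is weighted, and variable weights raise the variance of the log hazard ratio. It also carries the 2018 dabigatran count back to 2013, although 26 of the 76 enrolment months fall before the date the SAP gives for first-line access.

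Apixaban, rivaroxaban and edoxaban use the same method. Dabigatran is the smallest arm with the lowest share, and at HR 0.69 it has little slack. At stake is the go/no-go decision for Phase II. The plan gives no method for the Phase I power calculation, so section 9 is its only template. If the dabigatran comparison ran with less power than claimed, an imprecise null result could be read as no difference in bleeding.

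**Working it through.** **Inputs from the documents.** Two-sided alpha 0.05; 80% power; HR 0.69 (and 0.52); event probability 0.014; share p = 0.168; 866 dabigatran and 4,299 warfarin starters a year; 76-month window; access from May 2015 (26 months before, 50 after).

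**1. Reproduce the plan's figure.** Schoenfeld: N = (1.96 + 0.84)² / [p(1 − p)(ln HR)²] / 0.014.

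- HR 0.69: 7.84 / (0.168 × 0.832 × 0.1377) = 407 events; / 0.014 = 29,098 (stated 29,071).
- HR 0.52: 9,369 (stated 9,361).

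Agreement within 0.1% leaves no room for a weighting or trimming term.

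**2. Margin.** 36,162 / 29,071 = 1.24. Power = Φ(√[D p(1 − p)] × |ln HR| − 1.96), with D the number of events. The stated arms sum to 36,155 (the difference from 36,162 is rounding), so D = 506 and p(1 − p) = 0.1396. Then √70.6 × 0.371 − 1.96 = 1.16, and power is 87.7%.

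**3. Actual window only.** 866 × 76/12 = 5,485 and 4,299 × 76/12 = 27,227, total 32,712. Power is 84.3%, and the margin falls to 32,712 / 29,071 = 1.13.

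**4. Access date (assumed early use).** Let f be dabigatran use before May 2015 as a fraction of the 2018 rate, with the 2018 rate thereafter. Dabigatran users = 866 × (50 + 26f)/12. Column A holds warfarin at 27,227. Column B moves the missing starters of all four NOACs to warfarin: the 2018 sample has 83 + 264 + 57 + 26 = 430 NOAC starters, × 33.33 = 14,332 a year, so 14,332 × (1 − f) × 26/12 patients are added.

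| f | Dabigatran users | Power A | Power B |
|---|---|---|---|
| 0% | 3,608 | 69.8% | 72.6% |
| 50% | 4,546 | 78.2% | 80.4% |
| 65% | 4,828 | 80.3% | 82.0% |
| 100% | 5,485 | 84.3% | 84.3% |

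For f = 0 in column A: D = 30,835 × 0.014 = 432, p = 0.117, √44.6 × 0.371 − 1.96 = 0.52.

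**5. Weighting (assumed spread, stated projection).** Dividing D by a variance inflation of 1.2, 1.24, 1.3 and 1.5 gives 81%, 80%, 78% and 72%, so the break-even is about 1.24. To see what PS spread that implies, take a logit-normal PS with mean 0.168 and 1% trimmed. The Kish effective fraction of the dabigatran arm is 1 / (mean PS × mean of 1/PS); the warfarin arm uses 1 − PS in the same way. Inflation is the ratio of (1/n₁ + 1/n₀) at the effective sizes to the same sum at 6,062 and 30,093.

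| SD of logit PS | Effective fraction, dabigatran | Inflation | Power |
|---|---|---|---|
| 0.5 | 0.85 | 1.16 | 82% |
| 0.75 | 0.70 | 1.39 | 75% |
| 1.0 | 0.53 | 1.79 | 65% |

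**6. Other end of the HR range.** At HR 0.52 with 3,608 users (f = 0), power is 99%.

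**7. Detectable HR at 80% power.** exp(−2.80 / √[D p(1 − p)]): 0.72 on the stated counts, 0.70 on the 76-month window, 0.68 and 0.66 with f = 50% and 0% (column A).

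**The case against.** The strongest reply is that nothing here shows a shortfall. The documents give no PS distribution or variance inflation, and at the mild end of the assumed spread power is still about 82%. May 2015 is when all NOACs became available first-line; the SAP does not say that dabigatran was unused before. Power holds at 80% if early use was about 65% of the 2018 rate, or about half if displaced patients took warfarin. Moreover, section 9 is a pre-data projection. Phase I promises a detailed power calculation, SAP section 10 already tabulates index anticoagulant shares by calendar year and quarter, and a whole-database study makes no recruitment decision from this text. All of that stands and limits the weight of the point. It does not rescue the unconditional sentence, because a later calculation with no stated method cannot support a present claim of sufficiency.

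Three stronger readings are tempting and should be resisted:

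- A reader might infer that dabigatran weights averaging about 6 (1/0.168) shrink the arm. They do not: equal weights of 6 would leave the effective size at 6,062. Only variation in the weights costs precision.
- A reader might infer that the comparison is bound to be underpowered. The documents support only that it can be.
- A reader might infer an arithmetic slip in the required sizes. They reproduce; the weakness lies in what the formula and the projection leave out.

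**Conclusion.** The point holds in conditional form. At HR 0.69 the dabigatran claim rests on a 24% margin that the plan's own text erodes. The real enrolment window alone lowers power from about 88% to 84%. Beyond that, the result depends on two quantities the documents do not give. Across 0% to 65% early use, power runs from about 70% to 80% with warfarin at its 2018 level, or about 73% to 82% with displaced patients on warfarin. These ranges assume the 2018 dabigatran rate from May 2015 onward and a 1.4% event probability throughout. For weighting, inflation above about 1.24 is enough to fall below 80% on the stated counts, and above about 1.13 on the 76-month window. The two could be linked, because index year is a listed confounder: a steep rise in use would itself spread the weights. The concern does not extend to HR 0.52.

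**What to change.** In SAP section 9 and Protocol sections 4 and 9.5:

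1. Replace the 2018 count times seven with projections by year over the 76-month window, stating the assumed dabigatran and warfarin use before and after May 2015.
2. Replace the unconditional sufficiency statement for dabigatran with the power range or the detectable HR, and correct the drug name in the HR 0.69 sentence.
3. State that the Phase I power calculation that gates Phase II uses observed counts and the Kish effective sample size of each arm after trimming. This needs only the fitted propensity score, not outcomes.

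The cost is restated, less favourable figures for dabigatran and a little more analysis in Phase I. No new patients or data are needed.
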